### **3. Abstract:**

Obesity treatment guidelines recommend comprehensive behavioral weight loss treatments as the first line approach for adults with either obesity or overweight with a weight-related comorbidity. However, the vast majority of adults who are eligible for these weight loss treatments do not initiate them, even when offered at no cost. For individuals who decline weight loss treatment, obesity guidelines suggest a focus on weight gain prevention. Unfortunately, existing interventions to prevent weight gain have the same characteristics that cause many individuals to reject weight-loss treatments in the first place, such as didactic-focused meetings and prescriptions for dietary and physical activity change. To prevent weight gain while overcoming these common barriers to engaging in weight management interventions, we propose an intervention that prescribes self-weighing but does not prescribe changes in diet or physical activity behaviors or require attendance at didactic-focused meetings. The potential of self-weighing to promote weight management is supported both by self-regulatory theory and empirical research. Promoting self-weighing may activate participants' self-regulatory skills, leading to spontaneous decisions to reduce calorie intake or increase physical activity, thus preventing further weight gain. The proposed intervention will also provide individuals with text message-based feedback to promote continued self-weighing and to motivate engagement with evidence-based resources for weight management at a time when they may be more open to using these resources—e.g., after experiencing a small weight gain. The current proposal will investigate the feasibility and acceptability of this low burden self-weighing intervention in order to prepare for a fully-powered, pragmatic randomized controlled trial. We will enroll 40 patients with either obesity or overweight with a weight-related comorbidity and who have declined to participate in a comprehensive behavioral weight management program. Participants will be asked to weigh themselves daily via a "smart" scale that transmits weight data directly to the study team via the cellular network. Every-other week, participants will be sent text messages providing brief feedback encouraging continued self-weighing. Moreover, if a small weight gain is observed, participants will be sent text messages aiming to engage them in commercial or community-based evidence-based weight management resources. In a single-arm design, all enrolled participants will receive the intervention for 12 months and will complete assessments at 3 and 12 months to assess feasibility and acceptability of the intervention and trial design, while weight will be obtained from participants' Electronic Health Records (EHR). We will evaluate our success in meeting pre-specified metrics for trial feasibility and intervention acceptability outcomes, including intervention enrollment, intervention satisfaction, and obtainment of weight data abstracted from participants' EHRs. We will also evaluate the success of the intervention in promoting regular self-weighing and use of evidence-based weight management resources.

#### **4. Background:**

Obesity and overweight affect two out of three American adults, and increase the risk for numerous diseases and premature mortality. These risks can be minimized by use of comprehensive behavioral weight-loss treatments, which are the recommended first-line treatment for adults with obesity or overweight with a weight-related comorbidity. However, 80–93% of affected adults reject these treatments, even when offered for at no cost. Research by our team and others indicates that treatment is declined because individuals see no benefit in didactic treatment, dislike in-person and/or group meetings, and have numerous barriers to changing their diet and physical activity. For individuals who decline weight-loss treatment, preventing weight gain is the recommended approach. Unfortunately, existing evidence-based interventions to prevent weight gain have the same characteristics that cause individuals to reject weight-loss treatments in the first place: many provide didactic group meetings and focus on changes in diet and physical activity. Thus, an alternative approach is needed to prevent weight gain in individuals who decline comprehensive weight-loss treatments. One such approach is to offer a lower-burden intervention. For example, an intervention could prescribe self-weighing but not require changes in diet or physical activity or attendance at didactic meetings.

The efficacy of self-weighing interventions to prevent weight gain has been supported both by self-regulatory theory and existing empirical research. However, what has not yet been investigated is the effect of a low-burden self-weighing intervention on preventing weight gain in adults with obesity or overweight, and particularly among those who decline behavioral weight-loss treatments. Thus, the current application proposes a pilot study to investigate the feasibility and acceptability of a self-weighing + text messaging intervention. In the proposed intervention, participants will be asked to weigh themselves daily using a “smart” scale that transmits weight measurements directly to the study team via a cellular network. In addition to receiving text messages every other week which provide feedback and encourage continued self-weighing, participants whose weight gain passes a specific threshold will receive an additional, tailored text message. This text message will encourage the use of low-cost evidence-based weight-management resources (e.g., online dietary trackers). Messages encouraging use of resources may be particularly impactful given that they will come at a time when participants may be more willing to consider using resources to manage their weight (i.e., due to recent weight gain). Further, evidence supports the importance of responding quickly to small weight gains in order to prevent larger gains over time. Participants in this intervention who self-weigh infrequently will receive tailored messages aiming to engage them in more frequent self-weighing or in using weight management resources. This intervention approach has high potential for implementation within health care systems given its low complexity and potential for low cost. Further, our preliminary data demonstrate that many adults who decline traditional weight-loss treatments are willing to enroll in this sort of low-burden intervention.

A large clinical trial is needed to test the effectiveness of the proposed intervention. However, prior to that, we need data on feasibility and acceptability of the intervention and trial design, particularly given that individuals declining weight loss treatments have rarely been studied.

## 5. Specific Aims:

**Aim 1:** Identify predictors of willingness to engage in a weight loss intervention and a weight gain prevention intervention.

**Aim 2:** Determine the feasibility of the trial and acceptability of the intervention. We will examine the following feasibility/acceptability outcomes: intervention enrollment, intervention satisfaction, and whether adequate weight data can be extracted from participants' EHR.

**Aim 3:** Evaluate whether the intervention can promote regular self-weighing and use of evidence-based weight-management resources.

**Overview:** This study has two parts. Part 1 is a 15–20-minute survey, which participants are paid \$10 for completing. Some participants will be offered a second survey one month later, which also pays \$10. Part 2 is a 12-month intervention that involves participants being sent a smart scale, asked to weigh themselves daily, and being sent text messages every other week with feedback on their weight and suggestions for weight management. Part 2 also involves obtaining weight from EHR for 3 years after enrollment. Part 2 participants are paid \$10 for each of two online assessments and \$20 for a qualitative interview, for a total possibility of \$40. Only a portion of participants who complete the first (survey) part of this study will be invited to the second (intervention) part. Participants from Part 1 will be asked if they agree to allow us to obtain weight data from their EHR for a period of four years and will be given an option to complete REDCap e-consent for this.

**Participants, recruitment, and enrollment.** We will recruit UF medical patients aged 18–70 years whose EHR records indicate either obesity ( $BMI \geq 30 \text{ kg/m}^2$ ) or overweight ( $BMI \geq 25 \text{ kg/m}^2$ ) accompanied by a weight-related comorbidity.

We aim to obtain a sample size of 40 participants for part 2 of this study (intervention). We will cease recruiting for part 1 (survey) when we reach that goal. Thus, we are not able to know our total sample size for the entire study in advance, though we estimate that it will be 200.

We will recruit via two approaches:

(1) Emails and letters sent to patients identified by an IDR query for patients who meet criteria related to weight/comorbidity and age, have BMI recorded in the past month, and who have consented to be contacted by researchers through consent2share. IDR will provide patients' names, emails address and mailing address so we can send them the Consent2Share recruitment letter, as well as their race and gender so that we can over-recruit minority individuals to ensure representativeness.

(2) Emails and letters to patients who have had an appointment in the prior month with a primary care provider (PCP) who has agreed to allow us to send emails to his/her patients. We will obtain the list of patients by conducting an IDR pull to identify patients with appointments in the prior month who meet weight/comorbidity and age criteria. IDR will provide patients' names, emails address and mailing address so we can send them the letter from their provider, as well as their race and gender so that we can over-recruit minority individuals to ensure representativeness of our sample. We will send a signed letter from the PCPs from the study email address.

Patient identified through Consent2Share or the IDR query who have email addresses will be sent one email and up to one letter; patients who do not have email addresses will be sent one mailed letter. The email or letter sent to participants will inform them about the study and inviting them to complete a survey, with a link provided to a REDCap survey in the email/letter. Once on the REDCap site, all interested participants will read a consent document (see waiver to documentation of informed consent for Part I) and indicate consent by clicking a button, which will then lead to the eligibility portion of the survey.

### Eligibility criteria (Part I)

#### *Inclusion criteria*

- Weight record in EHR from year prior to recruitment email with last BMI in EHR  $\geq 25.0 \text{ kg/m}^2$ .
- Age 18-70.
- Self-report of BMI 24.0-29.9  $\text{kg/m}^2$  with comorbidity ((hypertension, type 2 diabetes, pre-diabetes, dyslipidemia, sleep apnea) or self-report BMI  $\geq 30.0$ .
- Self-report weight  $\leq 375$  lbs (the maximum weight that BodyTrace scales can accurately detect is 397 lbs, thus 375 lbs provides a buffer to allow detection of at least 20 lbs weight gain).
- Self-reported of sending at least one text message per month for past 6 months.
- Able to read and understand English without help.

#### *Exclusion criteria*

- Currently enrolled in comprehensive behavioral weight loss treatment or lifestyle-focused research study.
- Has engaged in self-weighing  $\geq 5$  times per week over prior month.
- Pregnant, breastfeeding, or planning to become pregnant in next 6 months.
- Currently undergoing radiation or chemotherapy for cancer.
- History of Congestive Heart Failure or heart attack in past 6 months.

- History of eating disorder.
- Planning to move out of the region in the following 12 months.
- Answer incorrectly on an attention check/ validation survey item.
- Report unwillingness to use data plan for this study.

Participants will be identified as eligible or ineligible for the intervention component (Part 2) based on responses of the survey study (Part 1, including one-month follow-up). The criteria for eligibility (in addition to being eligible to complete the survey) are:

- Respond “No” to question asking if they would like to enroll in a comprehensive weight loss program in the next month. AND
- Respond “yes” to question asking about interest in a self-weighing weight gain prevention intervention.

OR

- On the one-month follow-up Part 1 survey, respond that they have not enrolled in a weight loss program in the prior month, and that they are interested in a self-weighing weight gain prevention program

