## Procedures

Participants who are eligible for the survey study (Part 1) will be directed to the main survey on REDCap. Survey instruments include: Center for Epidemiological Studies-Depression (CES-D), Yale Food Addiction Scale, Social Phobia Scale (SPS-6), Weight Bias Internalization-Modified (WBIS-M), Perceived Treatment Efficacy, Barriers to Help Seeking Scale (BHSS), Financial Stress Measure, Experience of Racism, Stanford Leisure-Time Activity Categorical Item (L-CAT), as well as individual questionnaire items regarding weight loss history, and effects of COVID-19 on health.

Participants who are eligible for the intervention (Part 2) will be immediately linked to a brief introduction to part 2 of this study at the end of the survey and asked to share their contact information (phone number and email address) if they are interested. Research staff will call participants who are eligible and will review the consent form and answer any questions they have about the study and confirm their interest. The participants will be presented with the full informed consent document and consent to participate via signature provided through a REDCap e-consent. After completing this consent, they will be considered enrolled in the intervention.

Participants who indicate interest in the weight loss program will be informed that they will be sent a second survey in one month. They will be asked if it is ok to use the email address they provide for human subject payment to send them this second survey. This survey will ask them if they have joined a weight loss program in the past month, perceived barriers to joining weight loss programs, and if they are interested in the self-weighing program at that time. If they have not joined a weight loss program

and are interested in the self-weighing program, they will be linked to a brief introduction to part 2 (self-weighing intervention) of this study at the end of the survey and asked to share their contact information. Procedures to consent and enroll them in part 2 will be as described above.

After a participant consents to part 2, they will be sent a standalone questionnaire, called the eating disorder examination questionnaire (EDE-Q). This will be sent to the participant's email address via the REDCap platform.

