#### **Part 1 one-month follow-up survey**

- Study-specific questions about their interest in weight loss programs, and their barriers to joining weight loss programs.

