Data obtained during video- or audio-recorded interviews may be used in future publications but will not be linked with names or identifying information. The audio file will be downloaded from Zoom, saved on a password protected computer in our University office, and transcribed for responses to the questions. No names will be included on the typed files. If any personal information comes up during the interview, the information will be redacted from the transcript. Quotes from the interview may be used in future publications, but will not be linked with names or identifying information. All audio recordings will be deleted from the network drive where it will be stored, with assistance from the IT department once they have been de-identified and transcribed, no later than 12 months after they are recorded.

Another area of risk for this study is the potential for patients to engage in unhealthy or risky health behaviors while pursuing weight loss. Because this study does not provide close supervision by trained professionals and patients may encounter suggestions from the support network that are not consistent with guidelines. This risk is not dissimilar, and is likely lesser, from what individuals encounter when they

attempt weight loss on their own, which over 50% of adults with obesity report attempting in a given year.

Further, it is generally unsafe for women who are pregnant to engage in weight loss efforts, and it is an exclusion criteria in our study. As such, participants will be withdrawn from the study if they become pregnant.

Some participants may find self-weighing to be aversive. However, those participants will have the chance to decline enrolling in the intervention or to withdrawal from the intervention. Although it is possible that regular self-weighing may be aversive to some individuals who enroll, past research clearly demonstrates that there is no increase in eating disorder symptomatology among individuals assigned to daily self-weighing.

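### Pregnancy plans are screened 6 months ahead for a 12-month intervention, so some foreseeable withdrawals can enroll; one question at the Part 2 consent call would close most of the gap

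*Combined protocol and SAP*

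**What the plan says.** In the combined protocol and SAP, pregnancy appears as an entry criterion once, in the Part 1 list under Exclusion criteria: "Pregnant, breastfeeding, or planning to become pregnant in next 6 months". The same list looks a full year ahead for relocation: "Planning to move out of the region in the following 12 months".

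Part 2 eligibility builds on Part 1: "The criteria for eligibility (in addition to being eligible to complete the survey) are". The added items cover declining a weight loss program (or not having joined one by the one-month survey) and interest in the self-weighing program. The Overview in section 5 (Specific Aims) states that "Part 2 is a 12-month intervention".

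Two contacts between the Part 1 screen and Part 2 enrollment are described, and neither is said to ask about pregnancy again:

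- Under Procedures, the one-month survey is described as follows: "This survey will ask them if they have joined a weight loss program in the past month, perceived barriers to joining weight loss programs", plus interest in self-weighing. Its entry under Assessments and measures reads "Study-specific questions about their interest in weight loss programs, and their barriers to joining weight loss programs".
- Before Part 2 e-consent, "Research staff will call participants who are eligible and will review the consent form".

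Section 6 (Possible Discomforts and Risks) explains that "it is generally unsafe for women who are pregnant to engage in weight loss efforts". It withdraws participants who become pregnant and sets no time limit on that rule.

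**The concern.** The entry screen and the withdrawal rule cover different periods. The withdrawal rule applies throughout the intervention, while the planning question reaches only its first half at best. A person who already intends to conceive in, say, month 8 meets every written criterion, yet would be withdrawn if the plan succeeds. The protocol gives no reason for the shorter horizon.

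Two modest things are at stake. The first is avoidable attrition: a withdrawal foreseeable at entry uses up one of 40 places in a pilot about feasibility. The second is safety in the interval between conception and the study team learning of it. During that interval the rules under Intervention could treat pregnancy weight gain as a reason to offer weight-management resources.

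**Working it through.** No figure in the plan needs reproducing. The target of 40 rests on unspecified feasibility standards and is not in dispute. The check compares time horizons.

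**Inputs**
- Planning window: 6 months from the Part 1 survey (Exclusion criteria).
- Intervention length: 12 months (section 5, Overview).
- Lag L from the Part 1 answer to enrollment: taken as 0 for direct entrants (the most favorable case) and about 1 month for follow-up entrants (Procedures).
- Part 2 target: 40 (Sample size).

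**Step 1. Months of intervention outside the planning window**

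Uncovered months = 12 − (6 − L).

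| Route | L | Window left | Uncovered months | Share of the year |
|---|---|---|---|---|
| Direct | 0 | 6 | 12 − 6 = 6 (about months 7–12) | 6/12 = 50% |
| One-month follow-up | 1 | 5 | 12 − 5 = 7 (about months 6–12) | 7/12 = 58% |

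The shares are calendar time. They are not the probability that a participant is affected.

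**Step 2. After the change**

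A 12-month question at the consent call leaves 12 − 12 = 0 months uncovered, apart from any delay between the call and delivery of the scale. It also replaces the follow-up entrants' month-old answer.

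**Step 3. How much it could matter**

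No pregnancy rate is given, so the rates below are assumptions. They cover withdrawal for any pregnancy; the new criterion could prevent only the part planned beyond the current window.

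| Assumed rate | Expected withdrawals (40 × rate) | Chance of at least one, 1 − (1 − rate)^40 |
|---|---|---|
| 1% | 0.4 | 0.33 |
| 2.5% | 1 | 0.64 |
| 5% | 2 | 0.87 |
| 10% | 4 | 0.985 |

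Effect on precision, using the 95% half-width 1.96 × √(0.25/n) for a proportion of 0.5: 15.5 points at n = 40, 15.7 at n = 39 and 16.3 at n = 36. Even four losses cost less than one point.

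**Step 4. Effect on the weight summary**

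One case can raise the portion gaining at least 3% by at most 1/40 = 2.5 points. That requires a gain of 3% before the pregnancy is reported, inclusion of those weights, and no such gain otherwise. If the true portion is 20–30% (assumed), its standard error is √(0.20 × 0.80/40) = 6.3 to √(0.30 × 0.70/40) = 7.2 points. One case is then 0.40 to 0.35 of a standard error.

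**The case against.** The strongest reply is that pregnancy is already handled in two layers: exclusion of current or near-term pregnancy, then withdrawal whenever pregnancy occurs. Nothing obliges an entry horizon to match the intervention's length. The relocation item concerns a different matter, and 12 months is not total follow-up either, since EHR weights run for 3 years. The intervention prescribes no diet or activity change, its resources are optional, and the weight-gain messages ask willingness first.

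Much of this stands. The relocation item shows only that a 12-month horizon was workable elsewhere in the list; it sets no rule. The safety exposure is limited. But the withdrawal rule acts only once a pregnancy is known, and it cannot prevent a withdrawal that was foreseeable at entry.

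A reader might infer more than the documents support:

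- *That Part 2 has no pregnancy screen.* It has one, because Part 1 eligibility carries over. Only the horizon is short.
- *That half or more of participants are at risk.* The 50% and 58% are parts of the year, not of the sample.
- *That the weight results would be materially distorted.* The 2.5 points per case rests on an assumed case and several further conditions. Weight change is descriptive, and the primary goal is feasibility and acceptability.
- *That participants are not told to report a pregnancy.* The consent pages, survey forms and message library are not available and may say so, or may already repeat the pregnancy question. The mismatch lies in the written criterion itself.

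**Conclusion.** The mismatch is real and minor. As written, the plan can enroll people whose own stated intentions would trigger its withdrawal rule: about months 7–12 for direct entrants and about months 6–12 for follow-up entrants. This follows from the criteria and the intervention length, assuming that the follow-up answer is about a month old and that no unseen form repeats the question.

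The number of people affected cannot be derived from the documents and is probably small. No stated figure changes, the sample size is unaffected, and the loss of precision is slight under any rate tried above. The benefit is modest: fewer avoidable withdrawals and somewhat better safety. It is an optional improvement, and it does not show that the current plan is unsafe.

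**What to change.** Leave the Part 1 criterion unchanged, so that the Aim 1 survey sample is not affected. Under Exclusion criteria, add to the Part 2 list: *not pregnant, and not planning to become pregnant in the next 12 months*. Ask it at the consent call already described under Procedures, for both entry routes.

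The cost is one criterion and one question on a call that staff already make. The downside is that a few people identified as eligible and interested become ineligible for Part 2, which slightly lowers the enrollment yield reported under Aim 2. Count them as ineligible rather than as declining, so that the acceptability reading of that outcome is not affected.

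Keep the withdrawal rule, because a planning question cannot screen out unplanned pregnancies. Pregnancy items on the 3- and 12-month surveys are not needed for this change: month 3 falls inside the window already screened, and month 12 comes too late to stop messages.
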